9.4 STATISTICAL ANALYSES

9.4.1 GENERAL APPROACH

All analyses will be descriptive. We will calculate the proportion and 95% CI among enrolled infants with confirmed genetic disorders detected by NewbornDx, by rWGS, by NewbornDx but not rWGS, and by rWGS but not NewbornDx. We will also calculate the 95% CI for the ratio of the proportion detected by NewbornDx relative to the proportion detected by rWGS⁶⁹. Although detection by SOC is an exclusion criterion, some infants will receive a diagnosis by SOC after enrollment. We will therefore also calculate the proportion and 95% CI of those receiving a diagnosis by SOC prior to the time that results from NewbornDx or rWGS become available. We will calculate the proportions and CIs for enrollees with no confirmed diagnosis of a genetic disorder. These will be calculated at discharge and at 1 year CGA. We will calculate the proportion of infants with conditions detected by NewbornDx that were not listed as part of the differential diagnosis at enrollment. The same calculation will be performed for rWGS. We will calculate the positive predictive value (PPV) of NewbornDx and rWGS (i.e. the proportion of positives that are confirmed by Sanger or PCR).

Because a “gold standard” does not currently exist, it will not be possible to calculate the negative predictive value (NPV), sensitivity, or specificity of NewbornDx or rWGS. We will calculate the proportion for which there was clinical utility from genomic testing (change in drug treatment, surgical treatment, imaging, subspecialty consult, diet, other treatment, and redirection of care and/or withdrawal of life sustaining treatment). We will also calculate the proportion of testing where trios were ultimately required to confirm a diagnosis for rWGS and if this approach increased the number with a confirmed diagnosis. Kaplan-Meier (K-M) curves will be used to estimate the time from enrollment to molecular diagnosis (separately for NewbornDx and rWGS) including all enrolled infants and excluding infants without a diagnosis of a genetic disorder and those diagnosed by SOC before genomic results are returned. The analysis will count as positive only those diagnoses that are eventually confirmed. We will also use K-M to estimate age at diagnosis and survival. A model will be developed to predict, using information available at the start of symptoms, whether the NewbornDx ultimately yields a confirmed and actionable diagnosis. Such a model could help to further target NewbornDx to the population that would benefit most from it, especially if the model discrimination is high (c-statistic greater than .90). The model will be validated using bootstrap validation.

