2.2 BACKGROUND

[figure not shown]

Figure 1: Comparison of diagnostic yield for standard of care (blue), exome/genome sequencing (grey), and in silico TNGS panel (orange) for 254 patients across three publications

In-silico comparison of diagnostics rates demonstrate that a rapid neonatal NewbornDx (aka TNGS) panel may detect up to 90% of the same disorders as WGS at substantially lower cost (Figure 1).

We performed a retrospective in silico comparison of the 1,722 gene NewbornDx panel to already published rWGS and rWES clinical data from three studies representing 67 patients and 75 variants^{19,20,33}.

Compared to WES/WGS, the NewbornDx panel would have detected 85-94% of the same variants. A rapid NewbornDx panel using DBS has already been clinically validated under an SBIR Phase I grant through NICHD⁴². The panel is available as a laboratory developed test and is composed of 1,722 genes representing disorders that affect all systems (Figure 2), including all coding regions and clinically relevant non-coding regions.

NewbornDx panel would have detected 85-94% of the same variants. A rapid NewbornDx panel using DBS has already been clinically validated under an SBIR Phase I grant through NICHD⁴². The panel is available as a laboratory developed test and is composed of 1,722 genes representing disorders that affect all systems (Figure 2), including all coding regions and clinically relevant non-coding regions.

Figure 2. NewbornDx panel representing all 16 systems**Audiological**

Hearing loss (syndromic): 127 genes
Structural abnormalities: 24 genes

Cancer Predisposition

Neuroendocrine/CNS: 22 genes
Hematologic: 50 genes

Metabolic

Mitochondrial: 132 genes
Carbohydrate metabolism disorder: 23 genes
Lysosomal storage disease: 38 genes

Neurological

Brain malformations: 196 genes
Seizures: 304 genes
Microcephaly: 266 genes

Hematologic

Anemia: 82 genes
Bleeding disorder: 29 genes
Platelet disorder: 35 genes

Gastrointestinal

Large and small intestine: 10 genes
Liver disease: 42 genes
Failure to thrive: 18 genes

Skeletal

Short stature: 84 genes
Contractures: 31 genes
Bone fragility: 29 genes

Respiratory

Respiratory distress: 39 genes
Abnormal breathing: 12 genes

Muscle

Muscle atrophy/dystrophy: 44 genes
Hypotonia: 81 genes

Skin

Abnormal pigmentation: 25 genes
Abnormal hair and hair growth: 18 genes
Blistering: 18 genes

Endocrine

Adrenal dysfunction: 15 genes
Hypo-/hyper-glycemia: 44 genes
Hyper-/hypo-parathyroidism: 32 genes

Immune

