4 STUDY DESIGN

4.1 OVERALL DESIGN

This multicenter, prospective, clinical trial will estimate the diagnostic yield of NewbornDx and rWGS testing and assess the clinical utility of genomic sequencing among high-risk infants with signs/symptoms consistent with a possible genetic disorder. The relative cost effectiveness of each testing method will be evaluated through simulation.

There are three components to this study:

1. Infants will undergo SOC diagnostic testing as well as NewbornDx and rWGS in parallel. Genetic sequences via NewbornDx and rWGS will be generated for the infant (proband) and when available, the biological parents, and analyzed together. NewbornDx and rWGS test results will be returned to the infant's clinician, medical record and parent/guardian. Those infants analyzed as a duo or trio will have a retrospective analysis done of only the infant's data to determine if the same result would have been obtained with and without parent samples. Clinical utility will be measured by clinician opinion and changes in the infant's care as a result of the genetic sequencing test results. QoL and medical resource utilization will be collected by parent survey monthly, until the infant is one year CGA.
2. A retrospective chart review of neonates with suspected genetic disorders completed at 3 sites, will be used to elucidate 1-year cost and health outcomes that would have been incurred in the absence of available NewbornDx and rWGS testing. The retrospective review will include 300 neonates born 12-18 months prior to the start of the study and performed under a separately submitted amendment to the central IRB. The cost and health outcome data will be used in an economic evaluation comparing NewbornDx, rWGS, and SOC over 1-year and a child's lifetime time trajectory.
3. A user-friendly clinical reference database will be developed to provide medical providers and families with information about genetic disorders, treatments, clinical trials and advocacy groups. A qualitative assessment of the clinical reference database will be conducted through surveys of clinicians involved in the infants' care. Once the database is completed and prior to implementation of the clinical reference database into this study, an amendment will be submitted to the IRB along with the survey.

Hypothesis #1: NewbornDx will detect at least 60% of the diagnoses identified by rWGS

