9 STATISTICAL CONSIDERATIONS

9.1 STATISTICAL HYPOTHESES

The analysis plan is descriptive. There will be no statistical hypothesis testing.

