9.2 SAMPLE SIZE DETERMINATION

The sample proportion and 95% CI for the binary outcomes of NewbornDx and rWGS will be calculated. The table below shows the 95% confidence limits of the estimated proportion for a range of proportions, assuming the sample size is 400 completed infants. For example, if the sample proportion is 0.05 for disorders detected by rWGS but not NewbornDx, the 95% CI will be 0.03 to 0.07. Since the distribution of time to diagnosis is unknown, it is difficult to speculate as to the width of the confidence interval for the mean or median. However, 40% to 60% (160 to 240 infants) are expected to have a genetic diagnosis which is a sufficient number for a precise estimate.

Table: Confidence Interval Limits with 400 infants

Proportion	Lower Limit	Upper Limit
0.05	0.03	0.07
0.10	0.07	0.13
0.20	0.16	0.24
0.30	0.25	0.35
0.40	0.35	0.45
0.50	0.45	0.55

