9.4.2 ANALYSIS OF THE PRIMARY EFFICACY ENDPOINT(S)

Primary Endpoints	Definition	Scale and measure	Populations for which the analysis will be conducted
A confirmed positive result detected by NewbornDx	If NewbornDx and the confirmatory test have the same positive finding	Binary: Yes/No; single endpoint	Modified Intention-to-Treat Dataset
A confirmed positive result detected by rWGS	If rWGS and the confirmatory test have the same positive finding	Binary: Yes/No; single endpoint	Modified Intention-to-Treat Dataset
Time to a positive result by NewbornDx *	Among those who have a confirmed positive result at one year CGA by NewbornDx, rWGS, or another genetic test, comparison of date/time of sample collection to date/time of completion of NewbornDx prior to confirmation testing	Interval: Hours; single endpoint	Time to Molecular Diagnosis Dataset
Time to a positive result by rWGS*	Among those who have a confirmed positive result at one year CGA by NewbornDx, rWGS, or another genetic test, comparison of date/time of sample collection to date/time of completion of rWGS prior to confirmation testing	Interval: Hours; single endpoint	Time to Molecular Diagnosis Dataset
Time to a result by NewbornDx*	Among all babies tested, comparison of date/time of sample collection to date/time of completion of NewbornDx prior to confirmation testing	Interval: Hours; single endpoint	Modified Intention-to-Treat Dataset
Time to a result by rWGS*	Among all babies tested, comparison of date/time of sample collection to date/time of completion of rWGS prior to confirmation testing	Interval: Hours; single endpoint	Modified Intention-to-Treat Dataset
Time from enrollment to a positive result	Among those who have a confirmed positive results at one year CGA by NewbornDx, rWGS or another genetic test,	Interval: Hours; single endpoint	Time to Molecular

Primary Endpoints	Definition	Scale and measure	Populations for which the analysis will be conducted
detected by NewbornDx*	comparison of date/time of informed consent to date/time of completion of NewbornDx prior to confirmation testing		Diagnosis Dataset
Time from enrollment to a positive result detected by rWGS*	Among those who have a confirmed positive results at one year CGA by NewbornDx, rWGS, or another genetic test, comparison of date/time of informed consent to date/time of completion of rWGS prior to confirmation testing	Interval: Hours; single endpoint	Time to Molecular Diagnosis Dataset

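### Hypothesis #1 is about the share of rWGS diagnoses that NewbornDx also finds, but section 9.4.1 plans no estimate or interval for that share, only a ratio of yields that also counts NewbornDx-only positives

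*Combined protocol and SAP*

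**What the plan says.** Section 4.1 states: "Hypothesis #1: NewbornDx will detect at least 60% of the diagnoses identified by rWGS".

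Section 9.4.1 plans proportions with 95% CIs, taken among enrolled infants, for detection by each platform and for detection "by NewbornDx but not rWGS, and by rWGS but not NewbornDx". It then adds the "95% CI for the ratio of the proportion detected by NewbornDx relative to the proportion detected by rWGS", citing a paper on paired binomial proportions.

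Section 9.4.2 defines each platform's endpoint against its own confirmation test. For NewbornDx the definition is "If NewbornDx and the confirmatory test have the same positive finding", and the rWGS definition has the same form. Neither refers to the other platform's finding.

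Section 9.1 says "There will be no statistical hypothesis testing". No part of section 9 says which statistic addresses Hypothesis #1.

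**The concern.** The hypothesis conditions on an rWGS diagnosis and asks how often NewbornDx finds it too. The planned ratio divides all NewbornDx positives by all rWGS positives, so an infant diagnosed by NewbornDx alone raises the ratio although that infant is not among the rWGS diagnoses. The ratio can even exceed 1, which a share cannot.

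The plan states a numeric expectation without naming the estimate that answers it. The ratio is the only relative figure with a planned interval, so it is the one a reader is likely to set against 60%. It errs in one direction only, towards NewbornDx. Choosing between the two figures after the data are in would be post hoc, and they can fall on opposite sides of 60%.

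**Working it through.** **Notation.** n11 = infants detected by both platforms, n10 = by NewbornDx only, n01 = by rWGS only.

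- Hypothesis #1 share: S = n11/(n11 + n01)
- Planned ratio: R = (n11 + n10)/(n11 + n01)
- Difference: R − S = n10/(n11 + n01), which is zero only when n10 = 0

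**The plan's own precision figures.** The table in section 9.2 is p ± z·√(p(1−p)/400). At p = 0.05 and z = 1.96 this gives 0.029 to 0.071, matching the stated 0.03 to 0.07. Five of the six rows match to two decimals; the 0.30 row gives 0.255 to 0.345 against 0.25 to 0.35, a rounding-level difference that disappears with z = 2. The table covers single proportions of 400. It does not cover a share among rWGS positives.

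**What can be derived.** The point estimate follows from two planned proportions: S = 1 − p(rWGS only)/p(rWGS). Its CI cannot be read from the planned intervals, though it can be computed from the counts.

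**Inputs that are assumptions.** Section 9.2 says "40% to 60% (160 to 240 infants) are expected to have a genetic diagnosis". That is any genetic diagnosis; I use 160 to 240, with 200 as the midpoint, as an assumed number of rWGS positives. No NewbornDx-only rate is given, so n10 is varied.

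**Interval formulas.** Wilson for S. For R, a paired log-Wald interval with SE(log R) = √[(n10 + n01)/((n11 + n10)(n11 + n01))]. The Bonett-Price interval gives the same lower limits to two decimals for the three ratios in the table below.

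**Share of 55%, 200 rWGS positives** (n11 = 110, n01 = 90). S = 0.55, Wilson 0.48 to 0.62, whatever n10 is.

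| n10 | R | 95% CI for R |
|---|---|---|
| 10 | 120/200 = 0.60 | 0.53 to 0.68 |
| 20 | 130/200 = 0.65 | 0.57 to 0.74 |
| 30 | 140/200 = 0.70 | 0.62 to 0.80 |

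For n10 = 20, SE = √[110/(130 × 200)] = 0.065, and the lower limit is 0.65 × exp(−1.96 × 0.065) = 0.57.

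**How many NewbornDx-only positives change the reading at a 55% share:**

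| rWGS positives | R reaches 0.60 at n10 = | Lower limit of R passes 0.60 at n10 = |
|---|---|---|
| 160 | 8 | 23 |
| 200 | 10 | 27 |
| 240 | 12 | 30 |

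With 200 rWGS positives, 10 infants are 2.5% of 400. The 27 are 6.75% of 400 and 27/(110 + 27) = 20% of NewbornDx positives.

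**Share of exactly 60%, 200 rWGS positives, n10 = 20** (n11 = 120, n01 = 80). R = 140/200 = 0.70 with CI 0.62 to 0.79, wholly above 0.60. S = 0.60 with Wilson 0.53 to 0.67.

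**High overlap.** Section 2.2 reports, from retrospective in-silico work: "Compared to WES/WGS, the NewbornDx panel would have detected 85-94% of the same variants". At n11 = 170, n01 = 30, S = 0.85 (Wilson 0.79 to 0.89). R runs from 0.85 at n10 = 0 (lower limit 0.80) to 1.00 at n10 = 30 (lower limit 0.93). Both measures are well above 60%.

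**Precision of S at 0.60.** 96/160 gives 0.52 to 0.67; 144/240 gives 0.54 to 0.66.

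**The case against.** The strongest reply is that nothing depends on the 60%. The analysis is declared descriptive, the 60% is not an endpoint or success criterion in section 9, and the planned proportions with the known n fix every cell of the paired table, so anyone can compute the share later. That is true, and it limits the seriousness: no data are lost and the design is unaffected. It does not close the gap. A descriptive plan still needs to say which estimate speaks to its own stated number, and the share's interval is planned nowhere.

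Second, the example uses a 55% share, far from the in-silico 85-94%. The section 9.2 example of 5% rWGS-only (20 of 400), set against 160 to 240 rWGS positives, implies a share of 0.875 to 0.917. At such values the two measures agree about 60%. This stands, as does the point that moving the ratio's lower limit past 60% takes a sizeable NewbornDx-only fraction for which the documents give no support. Still, the in-silico figure is retrospective, from 67 patients and 75 variants, and the protocol itself chose 60% as its expectation.

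Third, matching of diagnoses across platforms may already happen: section 1 lists a Results Concordance form, and sections 6.1.1 and 8.2 describe how discordance is handled. The discordant categories in section 9.4.1 can also be read at the level of the disorder. The fair statement is that section 9 does not specify same-diagnosis matching, not that the trial ignores it. A variant called pathogenic by one laboratory and of unknown significance by the other is largely settled by the protocol's definition of a positive result, which requires a pathogenic or likely pathogenic classification.

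Finally, section 9.4.1 says "it will not be possible to calculate the negative predictive value (NPV), sensitivity, or specificity of NewbornDx or rWGS" for want of a gold standard. That does not block the share, which is agreement with rWGS and makes no claim about truth.

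**Conclusion.** The concern holds and should be fixed. Section 9.4.1 leaves the trial's first numbered hypothesis without a named estimate or interval, and its only relative statistic exceeds the relevant share by n10/(n11 + n01). That difference is exact. Its practical size is unknown because no NewbornDx-only rate is given. At a 55% share, 8 to 12 NewbornDx-only infants bring the ratio's point estimate to 60%, and 23 to 30 bring its lower limit above 60%, for an assumed 160 to 240 rWGS positives. If overlap is near the in-silico range, conclusions against 60% are the same either way. The ratio itself is legitimate as a measure of relative yield.

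**What to change.** In section 9.4.1, add n11/(n11 + n01) with a Wilson 95% CI among infants with a confirmed rWGS diagnosis, counting NewbornDx as detecting only when it reports the same confirmed diagnosis. Say at what level sameness is judged (variant, gene or disorder). Name this as the descriptive estimate for Hypothesis #1 and describe it as agreement with rWGS, not sensitivity. Keep the paired ratio as a separate measure of relative yield. No decision rule is needed.

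In section 9.2, add one line on the share's precision: at 0.60, a 95% CI of 0.52 to 0.67 with 160 rWGS positives and 0.54 to 0.66 with 240, stating that 160 to 240 is assumed from the range for any genetic diagnosis.

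The cost is about two sentences in 9.4.1, plus the definition of a match, and one line in 9.2. Both tests are run on every infant, so no new testing is needed. The Results Concordance form should support the matching, but its fields are not shown and should be checked. The downside is a relative figure that may be less favourable to NewbornDx than the ratio, with a wider interval than those in the table for 400 infants.

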6 STUDY INTERVENTION

6.1 STUDY INTERVENTION(S) ADMINISTRATION

6.1.1 STUDY INTERVENTION DESCRIPTION

NewbornDx and rWGS are CLIA/CAP certified and will be completed for all infants. The Athena (Quest) and RCIGM laboratories will be blinded to each other's result until all final results are returned.

Phenotype Extraction and Provision of Clinical Information to the Laboratories

1. A sub-group of clinicians from each site will manually review the medical record, extract relevant clinical information and determine the Human Phenotype Ontology (HPO) terms (refer to MOP). The sub-group of clinicians will consist of a minimum of 3 clinicians with at least one a geneticist or genetic counselor.
2. A small portion of the medical records (genetics consult note, other sub-specialty note (neurology, hematology, etc.) and NICU notes will be selected.
3. The HPO terms and medical records will be provided by the sites to the laboratories via upload to the RCIGM ordering portal. Athena will receive this data to its systems through a secure FTP site or encrypted email. Athena will not have access to the rWGS results through this mechanism.
4. Once HPO terms are submitted by the site, the laboratories may either add additional terms based on the last consult/progress notes submitted by the site or contact the site research team for clarification of symptoms. If this happens by either Athena (Quest) or RCIGM, the additional or revised HPO terms needs to be redirected to the site for upload to the portal. This ensures any new information is shared with both laboratories.

Athena Diagnostics (Quest)

NewbornDx Methods and Workflow

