Please refer to Section 6.1 Description of Study Intervention for details regarding the genomic sequencing methods that will be completed. Results of the infant's genomic testing will be shared with the research team, clinical team, the parent/guardian(s), and placed in the infant's medical record as follows:

Type of result	Result reported by laboratory	Action at site
Provisional Positive Result	Diagnostic findings related to phenotype - pathogenic variant(s) in genes interpreted to be responsible for, or contributing to, the infant's phenotype will be reported (classification of pathogenic or likely pathogenic). A provisional result means the result has not been confirmed. A provisional result is only given if waiting for confirmation testing would put the infant at risk for significant morbidity or mortality (a treatment is available and a delay would cause irreversible harm). For all provisional results, confirmation testing will subsequently be performed.	The enrolling site will receive management guidance by the laboratory and consult with their clinical genetics team. Provisional results will be entered in the infant's medical record under a research note. The research note will outline what provisional results were reported. Provisional results may guide the implementation of an intervention for the infant. Following clinical confirmation of results, a clinical report of the final result will be placed in the medical record. In the event that the positive finding cannot be confirmed, a research note will be added to the medical record to facilitate communication among multiple specialty services.
Confirmed Positive Result	Diagnostic findings related to phenotype - pathogenic variant(s) in genes interpreted to be responsible for, or contributing to, the infant's phenotype will be reported (classification of pathogenic or likely pathogenic). The result has been confirmed (for example with Sanger or qPCR). All positive results will be confirmed prior to return to the enrolling site with the exception of a provisional result.	Confirmed positive results will yield a clinical diagnosis, a referral to clinical genetics and reported in the medical record. Results may guide the implementation of an intervention for the infant.

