
The site PI/sub-I will speak with the physician of record and suitable subspecialists (for example, genetics, neurology, cardiology, etc.) at the time each test result is returned in order to review results and formulate a plan prior to returning a result to the parent/guardian.
 
The PI and/or sub-I at all sites are neonatologists or geneticists.
 
If the patient is discharged home prior to the return of results, the primary pediatrician should be contacted along with hospital clinical and research personnel.
	
Results will be disclosed to the family with as many members of the clinical team caring for the patient present as possible. At a minimum, each site will include one or more of the following: attending clinical geneticist, attending physician of record, attending neonatologist or geneticist who is a member of the study team. Additional attending subspecialists relevant to the particular genetic condition and genetic counselors may also participate in providing results to families. If clinical practice at a particular site is for licensed genetic counselors to return results without an attending physician as described above, the licensed genetic counselor may do so.
	
Recommendations to the family about changes in management or further genetic testing will be addressed by the physician of record as well as clinical genetics and other subspecialties per standard-of-care.
 
If a genetic problem exists that can be treated but does not need to be treated in the neonatal period, a referral to outpatient clinical genetics will be made.
	
It is strongly recommended that positive results or a VUS be disclosed in-person followed by a referral to a clinical geneticist. Depending on the need for timely action based on the results, it may be appropriate to return the result at the time of the next outpatient clinical genetics or related subspecialist appointment or to ask the family to come into the site to meet with the site PI to hear about the study results.
 
Under extraordinary circumstances (where the family lives hours away and/or has moved out of state), diagnostic or VUS results may be given by phone along with a clinical genetics referral. It is acceptable to convey negative/no finding results by phone with an offer for follow up genetic counseling visit.

Communication with a Biological Parent about a Parent Secondary Finding

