Upon the receipt of a report with a secondary finding for a biological parent by the site PI, the site will verify on the signed ICF that the biological parent opted-in to receive secondary findings. The result will be given to the biological parent by the enrolling site PI, study geneticist or genetics counselor and a referral to clinical genetics will be made. Some sites may opt to create a medical record for each biological parent and scan the consent and individual parental secondary findings to that medical record.

Genomic Sequencing Clinical Utility Survey

At discharge home or within one month after the return of results for infants who discharge home prior to the return of results, the physician of record at the time the results are returned will be asked to complete a brief survey regarding the clinical utility of the genomic testing. The one physician under whom the infant is admitted at the time results are received will receive the survey (i.e. neonatologist if the infant is in the NICU, pediatric critical care attending if the infant is in the PICU). The survey will be sent via email or a paper copy handed to the physician. The goal of the survey is to identify what changes were made to the immediate management of the infant as a result of testing as well as the general utility of the diagnosis. If the infant is discharged (home or death) prior to return of results, the Clinical Utility Survey should be completed by the clinical geneticist, most relevant subspecialist or by the site PI after speaking with the pediatrician (if baby was discharged home).

Parent/Guardian Contact Information, Medical Record Release and Diaries at Transfer/Discharge Home

The parent/guardian(s) will fill out a contact information form with multiple methods of contact to ensure we are able to reach the parent/guardian or primary care provider until the infant is 1 year CGA. A quality of life (QoL) instrument (The Optum™ SF-12v2® Health Survey) and the Child Visual Analog Scale will be administered.

Billing Information

At transfer to another facility and/or discharge home, the enrolling site research staff will obtain the final hospital costs and charges, and all physician CPT codes, for the infant's hospitalization.

Parent/Guardian Interview and Medical Record Acquisition

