2.0, 05DEC2019	The timeframe in which to collect the Clinical Utility Survey has been expanded to include at discharge home or for infants who discharge home prior to the return of results, within one month after the return of results.	To accommodate varying scenarios of when results are returned/acted upon.
2.0, 05DEC2019	In cases in which the infant is discharged home prior to the return of results, the Clinical Utility Survey should be completed by the clinical geneticist, most relevant subspecialist or by the site PI after speaking with the pediatrician.	To account for different physicians who will follow the subject and act upon results as an outpatient.
2.0, 05DEC2019	Physician CPT codes have been added to the types of data captured.	To better describe the types of billing data collected.
2.0, 05DEC2019	A parent may only opt-in to receive secondary findings if the parent/guardian opted-in for infant secondary findings. Inclusion of a table detailing the results returned for the infant and parent based on opt-in status, disorder onset, if the result is included on the ACMG59 or medically actionable.	To clarify under what circumstances a parent may opt-in for additional results and the possible results returned for the infant and parent.
2.0, 05DEC2019	Removed clinical geneticist as a required input to eligibility discussion. The study team will discuss eligibility of the infant	Depending on the site and condition, genetics is not always consulted per SOC.

	with the attending physician of record and if in agreement, the family will be approached for the study.	
2.0, 05DEC2019	The screening data captured in REDCap has been changed to replace maternal education and income level data with 5-digit zip code and primary symptoms with primary system involvement related to patient nomination.	The 5-digit zip code will be used in the health economic analysis. The change from clinical symptoms to primary system(s) involvement related to patient nomination of infants who have not provided consent is to reduce the risk of identification given the addition of zip code.

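### A new genetics referral that the protocol itself directs can count alone as clinical utility, and no planned figure gives the proportion with any other action

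*Combined protocol and SAP*

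**What the plan says.** **Endpoint.** Section 9.4.1 plans the proportion of infants with clinical utility and lists what qualifies: "change in drug treatment, surgical treatment, imaging, subspecialty consult, diet, other treatment, and redirection of care and/or withdrawal of life sustaining treatment". No item is excluded or weighted. The 9.4.2 table makes this a primary endpoint in the Modified Intention-to-Treat dataset. It has four parts: a yes/no on whether action followed from the results, the interval from result to action, the types of action, and the clinician's opinion.

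**Directed referral.** The result-type table in Section 8.2 says: "Confirmed positive results will yield a clinical diagnosis, a referral to clinical genetics and reported in the medical record". The table on communicating results, also in 8.2, adds two cases. For a treatable problem that does not need treatment in the neonatal period, "a referral to outpatient clinical genetics will be made". For infants who go home before results return, "It is strongly recommended that positive results or a VUS be disclosed in-person followed by a referral to a clinical geneticist".

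**Genetics as a subspecialty.** Section 8.2 has the site investigator consult "suitable subspecialists (for example, genetics, neurology, cardiology, etc" and others. Section 6.1.1 pairs "genetics consult note, other sub-specialty note" among the records sent to the laboratories.

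**Survey.** Section 8.2 says the clinician survey is meant to establish "what changes were made to the immediate management of the infant as a result of testing as well as the general utility of the diagnosis". It excludes no type of action.

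**Timing.** The synopsis ties the time component to starting suitable treatment or redirecting care. Section 9.4.2 times any action.

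**The concern.** A reader will take the yes/no proportion as how often results changed an infant's care. If a positive result triggers a step written into the protocol, and that step is on the list of qualifying actions, some infants become a yes because they had a diagnosis. Yield is already reported as its own primary endpoint, so to that extent the two figures would not be separate evidence. Section 9.1 plans no hypothesis test, so the reported proportion is itself the result and its definition carries the interpretation.

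The time component has a related problem. If a referral is an action, its date can become the action date, although the synopsis describes time to treatment or redirection of care.

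**Working it through.** **1. Can a referral alone score yes?**
- Section 9.4.2: one action due to the results is enough.
- Section 9.4.1: a change in subspecialty consult is on the list.
- Section 8.2: a genetics referral follows a confirmed positive.
- Sections 8.2 and 6.1.1: genetics is treated as a subspecialty.
- No section excludes a directed referral or requires a second action.

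The answer is yes where the referral is new to the infant. Such infants can exist: the Section 12 rationale for the current eligibility text notes, "Depending on the site and condition, genetics is not always consulted per SOC". That concerns the time before enrollment. The documents do not say how many infants are still unseen by genetics when results return.

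**2. Does a planned output isolate these infants?** Figures for drug or surgical changes contain no referral-only infants. But one infant can have several actions. The proportion with any action other than the referral therefore lies somewhere between the largest single-type proportion and the sum of those proportions, and the separate figures do not fix it. Sections 9.4.7 and 9.4.9 plan no such analysis.

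**3. The plan's own precision (Section 9.2, n = 400).** Half-width = 1.96 × √(p(1−p)/400).

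| p | Half-width | Limits | Plan's table |
|---|---|---|---|
| 0.20 | 0.039 | 0.161–0.239 | 0.16–0.24 |
| 0.30 | 0.045 | 0.255–0.345 | 0.25–0.35 |
| 0.40 | 0.048 | 0.352–0.448 | 0.35–0.45 |
| 0.50 | 0.049 | 0.451–0.549 | 0.45–0.55 |

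The table reproduces apart from rounding in the 0.30 row, which has no bearing here. The largest half-width is 4.9 points.

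**4. Size of the excess.** Inputs: 160 to 240 diagnosed infants of 400 (Section 9.2), and r, the share of diagnosed infants whose only recorded action is the genetics referral. The documents do not give r. I assume that the analysis set is 400.

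Excess = diagnosed × r / 400.

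| r | 160 diagnosed | 240 diagnosed |
|---|---|---|
| 0 | 0 | 0 |
| 5% | 8/400 = 2.0 points | 12/400 = 3.0 points |
| 8.3% (20/240) | – | 20/400 = 5.0 points |
| 12.5% (20/160) | 20/400 = 5.0 points | – |

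Twenty referral-only infants would move the estimate by about the largest half-width. This gives a sense of scale only. Sampling error is not a threshold for a choice of definition, and nothing in the documents says which r to expect. Infants with only a VUS who are referred after discharge would add to the excess. Their number is not given, so they are not sized.

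**The case against.** **Planned outputs already help.** Section 9.4.2 reports types of action and clinician opinion within the same endpoint. This stands, and it narrows the gap to one missing figure: the proportion with at least one action other than the referral.

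**A referral is not necessarily a counted change in consult.** Section 9.4.1 speaks of consults and Section 8.2 of referrals, and some passages list genetics beside the subspecialties instead of among them. The step is an inference. The documents do not separate the terms for scoring either, which is a reason to state the rule.

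**Genetics is often already involved.** The Schedule of Activities lists a genetics or specialty consult at screening per standard of care, and Section 8.2 has the investigator speak with relevant subspecialists as each result returns. For an infant already followed by genetics, a referral need not be a change. This stands and may make r small.

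**A first genetics consult prompted by a result can be a real change in care.** Agreed. It supports showing both figures and does not support dropping these infants.

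**Scoring may be settled elsewhere.** The Clinical Actions form, eCRF instructions, survey and manual of procedures are not in the documents reviewed and may hold a rule. What can be shown is that Section 9.4.1 states none.

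**A stronger reading to avoid.** A reader might infer that the utility proportion cannot fall below diagnostic yield, 40% to 60% on the plan's expectation. That would need every directed referral to be recorded as a change, including for infants already seen by genetics. The documents do not say so.

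**Conclusion.** The point holds as a minor one. On the stated rules, a new genetics referral directed by the protocol can by itself make an infant a yes on a primary endpoint, so the utility proportion can partly restate yield. The existing breakdown limits the harm without giving the one figure that would separate the two.

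The size is not known. It is yield times r, and r may be zero. The documents do not support any specific inflation figure, nor a claim that the endpoint is invalid or that no result free of referral-only infants is planned. The conclusion rests on reading a new genetics referral as a change in subspecialty consult, and on there being no contrary scoring rule in the documents not supplied.

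The mismatch between 9.4.2 and the synopsis on the time component can be read directly from the text and does not depend on r.

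**What to change.** 1. In Sections 9.4.1 and 9.4.2, state whether the protocol-directed genetics referral counts as a clinical action. If the Clinical Actions form, eCRF instructions, survey or manual of procedures already sets a rule, cite it.
2. Report the yes/no proportion with its 95% CI in two forms: any listed action, and any listed action other than a clinical genetics referral or consult. Keep the same denominator in both, so that referral-only infants move from yes to no and are not removed. Name the headline figure before analysis.
3. Reconcile the time component in 9.4.2 with the synopsis, so that a referral alone does not set the action date.

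If results are split by earlier genetics involvement, use involvement before return of results. The screening item in Section 8.1 covers only the time before consent and is at best a proxy.

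**Cost.** A few sentences and one table row. The team must check that the Clinical Actions form separates genetics from other consults; if it does not, a form field or record review is needed. The downside is a second, possibly lower, utility figure. Patient care does not change.
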